#### 7.4.1.4 Effect of centre

There is no analysis planned by centre due to the small number of patients to be recruited per centre.

#### 7.4.2 DINAMO Mono

The primary analysis will be a comparison of the treatment failure rates of linagliptin 5 mg, empagliflozin pooled and placebo (i.e. treatment grouping 1) using mITT set (NCF). The risk difference of active treatments versus placebo will be determined and assessed by an exact 2-sided 90% confidence interval based on the method of Chan and Zhang ([12](#)). Patients will be assigned to the treatment they were randomised to at the initial randomisation. Non-completers who prematurely discontinue intake of study drug will be considered treatment failures.

### 7.4.3 HbA1c data summary

An overall summary for the availability of HbA1c [%] data at Week 26 will be presented by TG1 on mITT (OC-AD) set showing captured and missing Week 26 data and further classified as on- and off-treatment and within these categories further sub-classified as 'without prior rescue' and 'with prior rescue'.

Frequency of patients who completed, altered or missed the HbA1c [%] measurement at Week 26 will be tabulated by TG1 on mITT set to assess the impact of COVID-19.

## 7.5 SECONDARY ENDPOINTS

### 7.5.1 Key secondary endpoints

This section is not applicable as no key secondary endpoints have been specified in the CTP.

### 7.5.2 (Other) Secondary endpoint(s)

#### 7.5.2.1 DINAMO

For the DINAMO secondary endpoints, the patients initially randomised to empagliflozin (empagliflozin 10 mg and empagliflozin 25 mg pooled) and linagliptin 5 mg will be compared versus placebo (i.e. treatment grouping 1). Analyses will be performed on the mITT set and will apply two approaches.

The *first approach* will use all observed data including data after premature discontinuation of study drug or post rescue medication data up to Week 26 (OC-AD).

Since FPG [mg/dL] is measured only at baseline and Week 26 within the analysis period, OC-AD-BOCF will be considered instead of OC-AD. The change in FPG [mg/dL] from baseline to the end of 26 weeks will be analysed using an ANCOVA model. This analysis will be repeated for FPG [mmol/L] in Appendix 16.1.13.

The statistical model will be:

$$\begin{aligned} \text{Change in FPG [mg/dL] from baseline to the end of 26 weeks} \\ = \text{overall mean} + \text{treatment} + \text{baseline FPG} + \text{categorical age at} \\ \text{randomisation} + \text{random error} \end{aligned}$$

Treatment is a fixed classification effect. Baseline FPG is a linear covariate and age at randomisation a categorical covariate. The random error is assumed to be normally distributed with mean 0 and unknown variance  $\sigma^2$ .

The other continuous secondary endpoints will be analysed based on a REML approach using MMRM. The analyses will include the fixed categorical effects of treatment, visit, and treatment-by-visit interaction, as well as the categorical covariate age at randomisation and the continuous, fixed covariates of baseline of the response variable and baseline of the response variable-by-visit interaction. The covariate visit will be treated as the repeated measure with an unstructured covariance structure used to model the within-patient measurements.

The Kenward-Roger approximation will be used to estimate denominator degrees of freedom and adjust standard errors. The residuals are assumed to have a multivariate normal distribution with zero means and covariance matrix as specified above.

Descriptive statistics up to the end of 26 weeks of FPG [mg/dL], weight [kg], SBP [mmHg] and DBP [mmHg] will be summarised by treatment grouping 1 and subgroup. See [Table 6.4:1](#) for the subgroups.

The proportion of patients who achieve  $HbA1c < 7.0\%$  and  $< 6.5\%$  at the end of 26 weeks will be determined per treatment grouping 1 using mITT (NCF) set and the risk difference of active treatments versus placebo will be determined and assessed by an exact 2-sided 95% confidence interval.

The *second approach* will include only on-treatment values measured prior to the start of any rescue medication up to Week 26 (OC).

The change in FPG [mg/dL] from baseline to the end of 26 weeks will be analysed using the ANCOVA model, which is described in the first approach, but using the second approach data.

For the other continuous secondary endpoints analyses, values measured after rescue therapy was initiated or after premature discontinuation of study drug will be set to missing. The missing data will not be imputed. The MMRM model will handle missing data based on a likelihood method under the "missing at random" assumption.

The proportion of patients who achieve  $HbA1c < 7.0\%$  and  $< 6.5\%$  at the end of 26 weeks will be determined per treatment grouping 1 using mITT (OC) set and the risk difference of active treatments versus placebo will be determined and assessed by an exact 2-sided 95% confidence interval.

#### 7.5.2.2 DINAMO Mono

The secondary endpoint of time to treatment failure will be analysed and graphically described by Kaplan-Meier estimates up to the planned end of the study (Week 52) by placebo in TG1, L5 and E Pooled in TG5. Patients in the placebo group will be censored after 26 weeks unless a prior treatment failure is observed. Data obtained after re-randomisation in the placebo group will not be utilised for the determination of time to treatment failure.

A descriptive Log-rank test will compare linagliptin 5 mg and pooled empagliflozin versus placebo individually up to Week 26 using mITT (NCF) set by treatment grouping 1. Patients will be censored after 26 weeks unless a prior treatment failure is observed.

The change in HbA1c [%] from baseline to the end of 26 weeks will be analysed based on a REML approach using MMRM to assess the effectiveness and efficacy, using the same sensitivity methods as described in [Section 7.4.1.3\(A\)](#) and [Section 7.4.1.3\(C\)](#) respectively. Analysis described in [Section 7.4.1.3\(C\)](#) will be repeated for HbA1c [mmol/mol] in Appendix 16.1.13.

It is expected that a large group of drug naïve patients will require early intervention of rescue medication as early as first on-treatment visit, therefore the change in HbA1c from baseline to the end of 26 weeks will also be analysed using an ANCOVA model including treatment as a fixed classification effect, baseline HbA1c as a linear covariate, and age at randomisation as a categorical covariate using mITT (OC-LOCF) set.

The following continuous secondary endpoints will be analysed using the same methods described in [Section 7.5.2.1](#), excluding the subgroup analyses.

- Change in FPG [mg/dl, mmol/L] from baseline to the end of 26 weeks
- Change in body weight [kg] from baseline to the end of 26 weeks
- Change in SBP [mmHg] from baseline to the end of 26 weeks
- Change in DBP [mmHg] from baseline to the end of 26 weeks

In addition, the change in FPG [mg/dl] from baseline to the end of 26 weeks will also be analysed using an ANCOVA model including treatment as a fixed classification effect, baseline FPG as a linear covariate, and age at randomisation as a categorical covariate using mITT (OC-LOCF) set.

The proportion of patients who achieve HbA1c < 7.0% and < 6.5% at the end of 26 weeks will be determined by treatment grouping 1 using mITT (NCF, OC) set and the risk difference of active treatments versus placebo will be determined and assessed by an exact 2-sided 90% confidence interval.

## 7.7 EXTENT OF EXPOSURE

An overall descriptive statistics table with mean, SD, median and range of the number of days a patient was on-treatment and patient-years together with the frequency count of on-treatment patients for the exposure in categories and exposure cumulative categories will be provided by TG1 and TG6. See Table 7.7: 1 for the presentation details.

Table 7.7: 1 Details for displays of treatment exposure, including exposure in categories and exposure cumulative categories

	Placebo comparisons period	Active treatment period
Treatment grouping	TG1	TG6
Period	Up to Week 26	Up to Week 52
Exposure in categories	>0 to 4 weeks, >4 to 8 weeks, >8 to 16 weeks, >16 to 24 weeks, >24 to 28 weeks, >28 weeks.	>0 to 4 weeks, >4 to 8 weeks, >8 to 16 weeks, >16 to 24 weeks, >24 to 32 weeks, >32 to 40 weeks, >40 to 46 weeks, >46 to 54 weeks, >54 weeks.
Exposure cumulative categories	≥1 week, ≥4 weeks, ≥8 weeks, ≥16 weeks, ≥26 weeks, ≥28 weeks.	≥1 week, ≥4 weeks, ≥8 weeks, ≥16 weeks, ≥26 weeks, ≥32 weeks, ≥40 weeks,

		≥46 weeks, ≥54 weeks.
First administration of study drug	Date of first study drug intake	Date of first active study drug intake
Last administration of study drug	Date of study drug intake at Week 26 minus 1 day	Date of last active study drug intake

In addition, the adjusted treatment exposure (treatment exposure minus total number of days of reported treatment interruption in relevant treatment period) will be summarised in descriptive statistics and patient-years by TG1 and TG6.

In order to assess the impact of COVID-19 to the treatment exposure in DINAMO only, the planned analyses for the treatment exposure will be repeated and summarised by permanent discontinuation of study medication or/and completed Week 26 visit before/from the start of COVID-19 disruption for up to Week 26 table and by permanent discontinuation of study medication before and from the start of COVID-19 disruption for up to Week 52 table.

A separate listing will be created of any patients that switched treatment at any time indicating exposure to the actual treatment against the randomised treatment.

All the above mentioned analyses will be presented for DINAMO and DINAMO Mono separately.

## 7.8 SAFETY ANALYSIS

### Primary safety analysis (Comparison vs. placebo) (up to Week 26)

The primary safety analysis will be based on the TS. All safety variables will be analysed from start of initial randomised treatment until Week 26 (except for AEs, which will be analysed up to the day before Week 26). The treatment grouping 1 will be used for the comparisons and presented for DINAMO and DINAMO Mono separately.

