Visit 4B could be a site visit or medication kits could be delivered at the patient's home by a dedicated study nurse/study site staff/delegated courier at the investigator's discretion and as per the local regulations. In case the medication kits would be delivered at the patient's home, a phone contact should be performed by a site staff representative. Following completion of the visit procedures, eligible patients will be re-randomised and the first dose of re-randomised trial drugs should be administered on the same day.

Re-randomisation at Visit 5 (Week 26)

After the 26-week treatment period, all patients will enter a double-blind safety extension period up to 52 weeks.

Patients who received placebo during the 26-week treatment period will be re-randomised to receive either linagliptin 5 mg or empagliflozin 10 mg or empagliflozin 25 mg. The re-randomisation will be stratified by age at baseline. At Visit 5, in order to preserve the trial blinding, the investigator will assign medication kits for all patients through the IRT system. Following completion of the visit procedures, eligible patients will be re-randomised and the first dose of re-randomised trial drugs should be administered on the same day

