7.3 PLANNED ANALYSES

The statistical analysis will be based on the following populations.

Treated set

The treated set (TS) will include all patients who are treated with at least one dose of randomised study medication. The TS is the basis for safety analyses.

Modified intention-to-treat set

The modified intention-to-treat set (mITT) will include all randomised patients who are treated with at least one dose of study medication and have a baseline HbA1c measurement. The mITT is the basis for the primary analyses.

Per protocol set

The per protocol set (PPS) will include all patients in the mITT set who do not have any important protocol deviations (IPD) which can be expected to have a distorting influence on the assessment of the primary endpoint. Details regarding the definitions of IPDs will be provided in the Trial Statistical Analysis Plan (TSAP) and the decision to exclude patients from the PPS will be made prior to database lock.

The term “baseline” refers to the following definitions according to the individual analysis period.

- *Study baseline*: Last observed measurement prior to administration of any initially randomised study medication at Day 1.
- *Titration baseline*: Last observed measurement prior to administration of the re-randomised study medication for the initial empagliflozin patients at Week 14.
- *Safety baseline*: Last observed measurement prior to administration of the re-randomised study medication for the initial placebo patients at Week 26.

For analyses up to Week 26, data collected after the first intake of study medication in the extension period will be censored.

Analyses up to Week 12 and Week 52 will be considered exploratory in nature. The study is not powered to compare empagliflozin with linagliptin at Week 12, Week 26 and Week 52, or to compare empagliflozin 10 mg with empagliflozin 25 mg at Week 52. No hypothesis testing is planned, and only descriptive statistics will be provided.

The anticipation for the patients who would have taken the wrong study medication is low. Therefore all analyses will be based on the randomised treatments. All patients with wrong study medication will be listed.

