#### 6.7 BASELINE, TIME WINDOW, AND CALCULATED VISITS

The term “baseline” refers to the following definitions according to the individual analysis period.

- *Study baseline*: Last observed measurement prior to administration of any initially randomised study medication at Day 1.
- *Titration baseline*: Last observed measurement prior to administration of the re-randomised study medication for the initial empagliflozin patients at Week 14. If last observed measurement is after rescue medication then there is no titration baseline for OC analysis.
- *Safety extension baseline*: Last observed measurement prior to administration of the re-randomised study medication for the initial placebo patients at Week 26.

Note: On or prior to date of randomisation will be used, instead of prior to date of drug administration, for randomised patients who have not taken any blinded study drug.

Both date and time of administration of the randomised study medication are expected to be recorded at Day 1, Week 14 and Week 26. In the determination of baseline for a parameter, if the parameter of interest:

- is collected with date and time: both date and time are used in the calculation of ‘last observed measurement prior to administration’. If the dates and times are equal, the parameter will be determined to be prior to administration.

- is collected with only date: the dates are equal, the parameter will be determined to be prior to administration.

The exception to this rule, is HbA1c, whereby even though time of sample is collected, it will be handled as if it was collected only with date.

Measurements taken after the first intake of randomised study drug will be considered on-treatment values if they have been obtained up to the end of the endpoint specific follow-up period as defined in [Table 6.7: 1](#).

Table 6.7: 1 Endpoint specific follow-up period for the assignment to treatment phase

Endpoint	Last day of assignment to treatment phase (days after study drug stop date)
Efficacy	
HbA1c	7
FPG	1
Body weight	1
BMI z-score	1
Blood pressure (systolic, diastolic)	1
UACR	7
Safety	
Adverse events	7
AESI Hepatic injury 	30
AESI Lower limb amputation	End of study
Safety laboratory measurements	7
AST/ALT/TBILI 	30
Pulse rate	1
C-peptide	1
Tanner staging	1

[1] Refers to a specific safety analysis including all hepatic injuries with an onset date up to 30 days after the study treatment stop.

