### 7.8.1 Adverse events

AEs will be coded using the latest version of the MedDRA coding dictionary at database lock.

Any clinically significant new finding in the physical examination, vital signs and in the 12-lead ECG starting after Visit 2 (randomisation visit) will be considered as an AE and will be reported as such.

Unless otherwise specified the analyses of adverse events will be descriptive in nature and analyses of AEs will be based on the number of patients with AEs (not the number of AEs). All AEs will be reported according to the BI standard (5).

AE outputs for TG4 and TG5 will be presented for DINAMO only in Appendix 16.1.13 unless otherwise stated.

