#### 7.8.1.1 Assignment of AEs to treatment

In general, the analysis of adverse events will be based on the concept of treatment emergent adverse events. This means that all adverse events occurring between first randomised or re-randomised drug intake until 7 days after last drug intake or cut-off (depending on analysis period, see [Section 7.8](#)) will be assigned to the randomised treatment.

In general, in-text AE tables will only present AEs assigned to the randomised treatment taken. For listings, AE will be assigned to one of the treatment phases of pre-treatment, treatment groups (depending on treatment grouping), post-treatment, post-study.

The cut off for the AEs outputs presentation period will be defined as the following.

- Prior to Week 26 treatment: Cut off at Visit 5 treatment date. If Visit 5 treatment date is not available, then the minimum of Day 183 or end of study date.
- Up to Week 52 present the whole treatment period plus the residual effect period.

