#### **7.8.4 ECG**

12-lead ECG measurements will be taken during placebo run-in, at Week 26 and at EoT (Week 52). Any clinically significant new findings in the ECG measurement after the first ECG will be considered as AEs and analysed as planned in [Section 7.8.1](#).

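### For patients who reach Visit 5 on treatment, adverse events first dated that day fall outside the placebo comparison, and the SAP does not settle where placebo patients' pre-dose findings go

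*SAP*

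**What the plan says.** **End of the placebo comparison.** SAP 7.8 (primary safety analysis) uses treatment grouping 1 (TG1: placebo, linagliptin, pooled empagliflozin) up to Week 26, "except for AEs, which will be analysed up to the day before Week 26". SAP 7.8.1.5 and 7.8.1.9 repeat the day-before end. SAP Table 7.7: 1 stops TG1 exposure one day before the Week 26 dose. SAP 7.8.1.1 gives the operational rule: "Prior to Week 26 treatment: Cut off at Visit 5 treatment date". Its fallback reads: "If Visit 5 treatment date is not available, then the minimum of Day 183 or end of study date".

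**How ECG and examination findings are analysed.** Under SAP 7.8.1, "Any clinically significant new finding in the physical examination, vital signs and in the 12-lead ECG starting after Visit 2" counts as an AE, and SAP 7.8.4 says the same for ECGs. The available SAP text describes no other analysis of either.

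**Timing.** The Flow Chart schedules ECGs at Visits 1B, 5 and 8, and physical examinations at Visits 1B, 2, 5, 8 and 9. Under Protocol 6.2.2 the Visit 2 assessments precede the first dose. At Visit 5 the procedures come first, then re-randomisation, and "the first dose of re-randomised trial drugs should be administered on the same day".

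**Protocol rule.** Protocol 7.3 states: "For analyses up to Week 26, data collected after the first intake of study medication in the extension period will be censored". Protocol 7.3.6 takes the placebo comparison to Week 26 with no separate end for AEs.

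**Active-treatment analyses.** SAP 7.8 leaves anything observed on placebo out of the active-treatment analysis (TG6). Protocol 7.3.6 limits initial-placebo patients there to data from after Week 26. SAP 6.1 defines the placebo column of TG9 (results disclosure) as placebo treatment up to re-randomisation.

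**The concern.** TG1 is the only randomised placebo-controlled safety comparison in the trial. A finding made at Visit 5 before the dose arises on the treatment that TG1 is meant to describe, but its date is the day of the extension dose, and the SAP stops counting AEs the day before. The protocol's own censoring rule would keep it.

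Two things are at stake. First, TG1 loses scheduled ECG and examination findings from patients who reach Week 26 on treatment but keeps those from patients who stop early, so what is ascertained depends partly on discontinuation. Second, for patients first randomised to placebo no rule says which period takes a pre-dose finding dated on the day of their first active dose.

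**Working it through.** No sample-size or power figure is involved. The check applies the date rules to AE onset dates.

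**1. Visit 5 date.** Week 26 is 26 × 7 + 1 = Day 183, which reproduces the Flow Chart day and the fallback cut-off in SAP 7.8.1.1. The ±7-day window gives Days 176 to 190.

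**2. Onset dates against the cut-off.** Let V be the date of the Visit 5 dose. TG1 AEs run from Day 1 to V − 1 (SAP 7.8 and Table 7.7: 1). If AEs are assigned by date alone, an initial-placebo patient's active period runs from V to last dose + 7 days (SAP 7.8.1.1). The results are the same for V = 176, 183 and 190:

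| Onset | TG1 under SAP 7.8 | TG1 if 7.8.1.1 alone is read as inclusive | TG6, placebo patient, date only |
|---|---|---|---|
| V − 1 | in | in | out |
| V | **out** | in | **in** |
| V + 1 | out | out | in |

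The inclusive reading goes against SAP 7.8, 7.8.1.5, 7.8.1.9 and Table 7.7: 1.

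**3. Findings that can carry date V.** After the first dose and before re-randomisation there is one scheduled ECG and one scheduled physical examination, both at Visit 5. For a patient who gets there on treatment, TG1 counts 0 of 1 for each when the finding is dated at the visit. The same applies to AEs first dated that day from other Visit 5 procedures:
- clinically relevant laboratory findings and dipstick-detected urinary infection (Protocol 5.3.3);
- ketones above 1.5 mmol/L (Protocol 5.3.5.3);
- laboratory-defined hepatic injury or decreased renal function (Protocol 5.3.6.1).

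**4. Early stoppers.** The early end-of-treatment visit also has an ECG and an examination. Take a last dose on Day 90 and that visit on Day 93. The AE limit is 90 + 7 = Day 97, so a finding on Day 93 is in TG1.

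**5. Initial-placebo patients.** SAP 7.8.1.1 assigns AEs from the re-randomised intake onward. If only the onset date is used, a pre-dose finding on day V counts as active. The TG6 exclusion in SAP 7.8, Protocol 7.3.6 and the TG9 placebo definition all say that data from the placebo period are not active data. If they prevail while the day-before cut-off stands, the TG1 and TG6 analyses both omit the event.

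**6. Whether time of day settles it.** Protocol 8.3.1 lists AE onset date as mandatory and mentions no time. SAP 6.1 uses time only where measured. For hypoglycaemia, SAP 7.8.1.5 assigns by start date alone. No general rule is given for other AEs.

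**7. Weight of one event.** With 50 patients per arm (Protocol 7.7.1), all treated, 1/50 = 2 percentage points of an arm's column.

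**The case against.** Stopping the day before a new drug starts is a recognised convention. It matches the TG1 exposure period and keeps possible new-drug events out of the placebo column. It applies equally to all three arms, so the cut-off alone favours none. ECG and examination results are not listed safety endpoints in Protocol 5.1.3.2. All of this stands, and it limits the point. It does not explain why findings made before the dose are excluded, when Protocol 7.3 draws the line after the intake. SAP 6.7 handles the same ambiguity the other way for baseline values collected by date only: if "the dates are equal, the parameter will be determined to be prior to administration". That rule selects measurements and does not govern AEs, so it is a precedent only.

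Four stronger readings are tempting, and the documents do not support them:
- **A reader might infer that Week 26 ECG and examination findings never count.** Early end-of-treatment findings, unscheduled ECGs (Protocol 5.3.4) and Visit 5 findings given an earlier onset date all count in TG1.
- **A reader might infer that placebo patients' findings are assigned to active drug.** This follows from SAP 7.8.1.1 only with date-only onset, and it conflicts with the other passages in step 5 of the working. The Protocol 8.3.1 list gives examples and does not establish that onset time is never collected.
- **A reader might infer that TG1 loses Week 26 laboratory, urine or vital-sign data.** The day-before limit is for AEs only; the values stay in TG1 (SAP 7.8.2 and 7.8.3). Infection capture does not rest on scheduled dipsticks either, since Protocol 5.3.3 asks for symptoms to be watched throughout.
- **A reader might put a figure on the shift in active-drug incidence.** The documents give no rate of new findings at Visit 5, and any such figure also assumes active assignment.

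**Conclusion.** The point holds in a narrow form. For patients who reach Visit 5 on treatment, AEs first dated on the Visit 5 treatment date are outside the TG1 comparison. These include new findings from the period's only scheduled on-treatment ECG and physical examination. This departs from Protocol 7.3, and SAP section 4 does not record it as a change. For initial-placebo patients the SAP conflicts with itself, and the same event could be counted as active or in neither period.

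The certain size is the coverage: 0 of 1 scheduled ECGs and 0 of 1 scheduled examinations. The number of AEs affected is unknown and probably small, but each weighs 2 percentage points in an arm of 50. The conclusion assumes that such findings are dated at the visit, that the dose is given that day as planned, and that the repeated day-before wording governs the shorter cut-off sentence in SAP 7.8.1.1. This is a cheap improvement to the safety analysis. Efficacy is not affected.

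**What to change.** Add one assignment rule to SAP 7.8, 7.8.1.1, 7.8.1.5 and 7.8.1.9:

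- AEs dated on the Visit 5 treatment date that arise from Visit 5 pre-dose procedures (ECG, physical examination, vital signs, laboratory or urine sample, site ketone check) belong to the treatment taken before re-randomisation. They count in TG1 and, for initial-placebo patients, not in TG6 or the active columns of TG9.
- Identify them by onset time where recorded, otherwise by blinded review before database lock.
- Leave other AEs dated that day with the new treatment, and list them.

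Then align the TG1 end in SAP 7.8, the TG6 exclusion, the cut-off in SAP 7.8.1.1 and the exposure end in Table 7.7: 1, so that all describe the same boundary.

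The cost is SAP wording, one programming rule, and a blinded review or source flag for the few AEs dated that day. No extra assessments of patients are needed.
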